Elevated glycemic levels are a primary predictor of later cardiovascular disease risk for adolescents with type 1 diabetes, with even a period of suboptimal glycemic levels contributing to persistent increases in later cardiovascular disease risk.³³ Yet, for those with type 1 diabetes and SED improvements in diabetes-self-management and glycemic outcomes alone do not entirely resolve health disparities in cardiovascular disease. This may be due to both increased prevalence of conventional cardiovascular disease risk-factors and type 1 diabetes-specific risk processes. First, adolescents with type 1 diabetes show early elevations in known cardiovascular risk factors, with 38% evidencing elevated low-density lipoprotein-cholesterol levels, 22% evidencing elevated blood pressure, and 39% evidencing overweight or obesity,²³ with increased rates of these risks present in adolescents with SED.^{34,35} In adults with type 1 diabetes, targeting conventional cardiovascular disease risk-factors, beyond glycemic levels, contributes to perhaps a 29% reduction in risk of death;³⁶ however, these risk factors are not typically assessed nor targeted in intervention programs for adolescents with type 1 diabetes. Additional risks for cardiovascular disease may be unique in persons with type 1 diabetes. For example, in adolescents with type 1 diabetes, combined elevations in high density lipoprotein and systemic inflammation together predict early progression of cardiovascular disease, such that inflammation is argued to disrupt the anti-inflammatory function of high density lipoprotein.³⁷ Interventions that specifically target both conventional cardiovascular risks and systemic inflammation might have increased potency for cardiovascular disease prevention in adolescents with type 1 diabetes and SED.

- d) Physical activity promoting interventions combined with diabetes behavior-change skills training might be particularly potent for targeting self-regulation, glycemic levels, and cardiovascular disease risk.

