All procedures will be conducted solely for research purposes. We will recruit 60 adolescents aged 13-17 years old with type 1 diabetes, through pediatric endocrinology clinics and via a national advertising recruitment method established with our research team that leverages Facebook, Instagram, and Google Ads resulting in a nationally representative sample. National advertising recruitment: Interested families will contact the research team. Pediatric endocrinology clinic recruitment: A clinic staff member will provide the same online information used in national recruitment about the study to the family during a clinic visit and interested families will be provided with instructions for how they can contact the research team if interested in participating. At the University of Vermont Medical Center pediatric endocrinology clinic, a member of the patient's care team will ask eligible families for permission to have one of our research team members enter to share our same recruitment flyer used in national recruitment about the study and instructions for how they can contact the research team if interested. Research staff will respond to interested families and explain the study procedures in greater detail to the adolescent and to the adolescent's legal guardian. If both agree, the research assistant will arrange for a call to complete the electronic informed consent and assent process through RedCap. After consent/assent, the adolescent and parent will complete the baseline video-based lab assessment and be mailed an assessment kit with all required tools for the assessment and program (dried blood spot assays, Garmin fitness activity tracker, measuring tape, electronic blood pressure cuff, scale). Families without a computer, tablet, or phone, will be provided a small tablet to use for assessments.

The baseline assessment will be conducted with the ongoing support of the research staff via a video conference using Larner College of Medicine Zoom with HIPAA-compliant settings and the parent available at home. There will be no video recording. First, the adolescent and parent will complete a set of online questionnaires (through RedCap), see descriptions below of measures. Second, the adolescent will complete the physical assessments:

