Dried Blood Spot Assay: A mail-in dried blood spot assay for cardiometabolic risk factors will be collected (Kapur ZRT Laboratory, 2008). Kits for blood spot collection contain a filter paper collection card, finger lancets, an alcohol prep pad, sterile gauze, a band-aid, easy-to-follow instructions, and a mailer to return the sample for analysis. The test kit will be included in the mailed assessment kit and adolescents will follow the instructions provided in the test kit with research assistant support for any questions. The test kit instructions will ask participants to provide a finger-stick blood sample on a collection card and to mail the dried blood sample (at least 3 hours dried) coded to the lab for storage before bulk processing at ZRT Laboratory. Please note that these test kits are commonly used by patients with diabetes and involve procedures that are similar to blood glucose monitoring that patients complete multiple times each day. Dried blood spot samples are also stable at room temperature for up to 1 month and dried blood spots are exempt from biohazard mailing regulations as with triple-packaging as provided in test kit there is no reasonable expectation of occupational exposure to blood (CDC, 2017). This procedure allows us to collect information about cardiometabolic risk factors from the

participants at home using a highly familiar finger stick blood test. We have successfully used this method of home testing in youths with type 1 diabetes in prior studies.⁸⁴

Abdominal Circumference: The assessment kit will include a measuring tape and instructions for measuring abdominal circumference at the midpoint between the bottom of the rib cage and the iliac crest and at the hip. Participants will be trained and then asked to measure the abdominal circumference. The participant will report and confirm on the measuring device the measurement to the research assistant.

Blood pressure: The assessment kit will include an electronic blood pressure cuff and the research assistant will provide instructions to place the cuff 1 inch above elbow with arm relaxed before starting the measurement. The participant will report and confirm on the measuring device the blood pressure to the research assistant.

Weight: The assessment kit will include a small digital scale and the research assistant will provide instructions for use. The participant will report and confirm on the scale the weight to the research assistant.

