Cardiovascular Disease Risk Score. We will assess per the American Heart Association Life's Simple 7 index, which includes weight, blood pressure, diet, physical activity, blood sugar, and cholesterol. We are excluding smoking which would not be anticipated to change in response to this intervention and has low base rates in adolescents with type 1 diabetes. Physical indicators will be assessed through the dried blood spot assay including total cholesterol and HbA1c. We will also assess weight, physical activity as well as systolic and diastolic blood pressure through our home-based virtual assessment protocol (see above). Last, we will ask the adolescent to report on diet habit using the standardized healthy diet questions from that match the American Health Association Healthy diet recommendations and they report if they tried or currently smoke. Cardiovascular health risks will be summarized through a single risk score. For each risk indicator, meeting ideal, intermediate, or poor health status will be associated with a score of 2 to 0, respectively, creating a 0 to 14 scale of cardiovascular disease risk.

TYPES OF PROCEDURES (Please do not use the "other" option unless the procedure is not listed.)

Check all that apply.

	Survey (mail, telephone, in-person, on-line)		Blood drawing: dried blood spots from finger stick	Vol.	10 drops of blood (30µL)	Over days, weeks?	Across two assessments 12 weeks apart (5 drops/ 15µL/assessment)
	Medical exams/history: blood pressure and abdominal circumference only					Type & Amt.	Dried blood spot card with 5 discs
	Deception *see below						Collection of Urine and/or Feces
	Observation						HIV Testing
	Photographs		Surgery				Ultrasound (e.g. echocardiogram)
	Audio Recording		Drug Administration				
	Video Recording		Device Use: Garmin fitness activity tracker				Imaging (e.g. CT scan, DEXA, mammogram, PET scans, SPECT)
	Interviews in person or by		Exercise				Use of Radiation treatment
			Diet				Use of Radioactive substances (e.g.
			Pathology Specimens				

phone		(retrospective)		radiolabeled antibodies, drugs or contrasts)
Focus Groups		Genetic Materials (DNA)** see below		MRI (for treatment studies)
Review of prospective data		Questionnaires		MRI (not for treatment studies)
Review of retrospective data		Diaries		Tissue (obtained for clinical purposes)

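### The weight item of the cardiovascular risk score must be graded ideal, intermediate or poor, but no height measurement or weight-status rule is described, so it cannot be validly graded at ages 13-17

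*Protocol*

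**What the plan says.** Under Secondary Health Outcomes, the paragraph on the Cardiovascular Disease Risk Score adopts a named public index, "which includes weight, blood pressure, diet, physical activity, blood sugar, and cholesterol". It applies one rule to all items: "For each risk indicator, meeting ideal, intermediate, or poor health status will be associated with a score of 2 to 0, respectively". It prints no cut-points for weight and sends the reader back to the home video assessment for the measurement.

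That assessment is described under Procedures. The mailed kit holds "dried blood spot assays, Garmin fitness activity tracker, measuring tape, electronic blood pressure cuff, scale". The Weight paragraph covers use of the scale and ends: "The participant will report and confirm on the scale the weight to the research assistant". The tape has one stated use: "The assessment kit will include a measuring tape and instructions for measuring abdominal circumference", with a second reading at the hip. The whole battery is repeated after twelve weeks.

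Aim 2 names the score as an outcome. Statistical Considerations lists it for analysis with baseline-residualized gain scores. The SAP does not mention it.

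**The concern.** To score the weight item, staff must turn each participant's weight into one of three health categories. In adolescents that judgement depends on body size, and the one body-size variable that would normally be paired with weight is absent from the described measurements. The protocol's own background, in Scientific Premise (c), speaks of this risk as excess weight ("39% evidencing overweight or obesity"). That is a population figure, not the trial's definition of the item, but it shows that weight status is meant, not kilograms.

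Without a height or a stated rule, three courses are open: leave the item out, take height from an unplanned source such as recall, or grade raw kilograms. Each gives a different score, and nothing says in advance which applies. Raw kilograms would misplace tall and short participants and could read ordinary growth as worsening. The gap is also hard to repair afterwards, because height at the time of each visit cannot be reliably recovered in participants who may still be growing.

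**Working it through.** This is mainly a check of the documents against themselves. The plan states no figure to reproduce.

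**1. Is height, or a substitute for it, described anywhere?** I looked through both documents for height, stature, BMI, percentile and z-score. None appears as a measurement, report or derived variable; the only string match is inside *heightened*, in the text on stress. No rule ties abdominal or hip circumference to the weight item. Abdominal circumference has a different stated job, as an input to the estimated glucose disposal rate.

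**2. Can kilograms stand in for weight status?** BMI = weight in kg / (height in m)². Weight and heights are illustrative assumptions, not trial data. For a 65 kg adolescent:

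- 150 cm: 65 / 2.2500 = 28.9
- 160 cm: 65 / 2.5600 = 25.4
- 170 cm: 65 / 2.8900 = 22.5
- 180 cm: 65 / 3.2400 = 20.1

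One scale reading spans 28.9 - 20.1 = 8.8 kg/m², so it does not determine weight status.

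**3. Is one height enough for both visits?** Hold weight at 65 kg, start at 160 cm and assume 0 to 2 cm of growth over 12 weeks. BMI goes from 65 / 1.60² = 25.4 to 65 / 1.62² = 24.8, a shift of about 0.6. That is small, but it can move a participant who is near a category boundary, so height is worth taking twice.

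**4. Would home-taped height be good enough?** With an assumed error of 2 cm either way around 160 cm, BMI ranges from 65 / 1.62² = 24.8 to 65 / 1.58² = 26.0, or about 0.6 either way. That is far narrower than the 8.8 in step 2.

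**5. How much of the score is affected?** The item is worth 2 points per participant per visit. Six listed items at 2 points give a maximum of 12, so the share is 2/12 = 16.7%. On the printed maximum of 14 it is 2/14 = 14.3%. The mismatch between 12 and 14 is a separate matter and does not affect this one.

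**The case against.** **Silence is not proof of absence.** A reader might infer that height is never measured. The documents do not support that. Diabetes technology use and length of diagnosis are model covariates, and socioeconomic disadvantage describes the sample, yet the protocol does not say how each is collected. Height could sit on a similar undescribed form. What stands is narrower: no height measurement or report is described, although Procedures itemises the physical measurements and the score paragraph points there for weight.

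**Some lists prove little.** The procedures checklist says "Medical exams/history: blood pressure and abdominal circumference only", and the visit time budget and Sources of Materials also omit height. All three omit weight too, which is plainly measured. The point rests on the Procedures text and the score paragraph alone.

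**The index's own weight criterion is not printed.** It may imply BMI, but the documents do not say so, and another rule, perhaps one built on the circumferences, is conceivable. This supports asking the sponsor to state the rule and its inputs. It does not remove the gap, because no rule is given.

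**The treatment comparison is largely protected.** A reader might infer that the Aim 2 contrast is biased. That does not follow. Stable height differences between participants would largely be absorbed by baseline adjustment, and growth over 12 weeks should be similar on average in randomised arms. What remains is misclassification and noise. The documents give no standard deviation for the score, so the loss of precision cannot be estimated.

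**The stakes are modest.** This is one item of one secondary composite, under an aim described as exploratory, in a 60-participant preliminary-efficacy trial. One research team runs the assessments, so the gap can be closed centrally.

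**Conclusion.** The point holds as a gap in specification that affects validity. The plan requires a weight category for up to 60 participants at two visits and describes neither the height nor the rule needed to assign it. One of six listed items, 2 points or 14-17% of the score's maximum depending on which total is used, cannot be validly graded from the described measurements. It does not show that the other items fail, and it does not touch the primary outcomes.

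The conclusion assumes that the weight item means weight status rather than kilograms, and that no undescribed form captures height. If the second assumption is wrong, the remedy shrinks to a sentence naming the form and the grading rule. It should be settled while visits are still to come, since heights missed at a visit cannot be dependably filled in later.

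**What to change.** - In Procedures, add standing height to the physical assessments at baseline and at 12 weeks, measured with the tape already in the kit, with the parent (who is to be at home) helping on video.
- In the Cardiovascular Disease Risk Score paragraph, state the rule that turns the measurements into ideal, intermediate or poor for the weight item, with cut-points and inputs. BMI for age and sex is one option; if another rule is intended, print it.
- Bring the time budget, procedures checklist and Sources of Materials into line by listing both weight and height.
- If height is already collected, name the form and the time points instead.

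The cost is a minor amendment and a few extra minutes per visit (assumption), with no new equipment. The downside is home-measurement error in height, assumed at about 1-2 cm.

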****If genetic information is being collected, GINA language must be added to the consent form.**

*Deception typically involves withholding information from the potential subject and would require an alteration to the consent process.

Statistical Considerations: Delineate the precise outcomes to be measured and analyzed. Describe how these results will be measured and statistically analyzed. Delineate methods used to estimate the required number of subjects. Describe power calculations if the study involves comparisons. Perform this analysis on each of the primary and secondary objectives, if possible.

In aim 1, we assess the feasibility and acceptability of the Activate program as well as its preliminary efficacy on behavior-change skills (goal-setting and coping skill efficacy) and average daily active minutes. To assess acceptability of the Activate program we will examine participant engagement with the Activate program components, including behavior skill training sessions completed and physical activity goals met, as well as qualitative and quantitative participant feedback on their experience with the program at the end of treatment. A priori benchmarks for acceptability, indicating no further revision is needed will be greater than 80% of sessions completed and physical activity goals met as well as more than 80% of participants providing positive feedback regarding willingness to participate again.

To assess the preliminary efficacy of the Activate program we will examine changes in proximal primary outcomes of goal-setting, coping skill efficacy, and average daily active minutes compared between treatment and control groups at baseline and the 12-week follow-up assessment. We will conduct multilevel models with baseline-residualized gain scores for outcomes to identify the effect size for the treatment program on each of the three primary outcomes. Each model will include the baseline outcome covariate as well as additional disease covariates including diabetes technology use and length of diagnosis. All participants will be used in analyses, with missing data addressed with full information maximum likelihood estimation. A power sensitivity function was generated wherein our pilot study analyses were used to determine expected effect sizes. Anticipated effect sizes based on our pilot work for between group differences in behavior-change skills and average daily active minutes are Cohen's d of 0.4 to 1.2. With 60 participants, we will have 80% power to detect a Cohen's d of .7, 60% power to detect a Cohen's d of .6, at 95% power to detect a Cohen's d of .8. Thus, we will be powered to detect all but the smallest of potentially meaningful effects found in our previous intervention pilot work.

In aim 2, we test the impact of the Activate program on secondary mechanisms of biobehavioral self-regulation systems and glycemic and cardiovascular disease risk outcomes closely linked with type 1 diabetes health disparities. To assess changes in putative mechanisms and secondary outcomes we will use baseline-residualized gain scores in multilevel models to identify the effect size for the treatment program on each of the secondary outcomes assessed for behavior regulation, distress, c-reactive protein, mean and variability in daily blood glucose, and cardiovascular disease risk score. For all analyses missing data will be addressed with full information maximum likelihood estimation. A power sensitivity function was generated wherein our pilot study analyses were used to determine expected effect sizes. Based on our pilot work we anticipate effect sizes from Cohen's d of .4 to .8 and thus with 60 participants, we will again have 80% power to detect a Cohen's d of .7, 60% power to detect a Cohen's d of .6, at 90% power to detect a Cohen's d of .8. We will be powered to detect all but the smallest of potentially meaningful effects found in our pilot work.

Risks/Benefits: Describe any potential or known risks. This includes physical, psychological, social, legal or other risks. Estimate the probability that given risk may occur, its severity and potential reversibility. If the study involves a placebo or washout period, the risks related to these must be addressed in both the protocol and consent. Describe the planned procedures for protecting against or minimizing potential risks and assess their likely effectiveness. Where appropriate, discuss plans for ensuring necessary medical or professional intervention in the event of adverse effects to the subjects. Discuss the potential benefits of the research to the subjects and others. Discuss why the risks to the subjects are reasonable in relation to the anticipated benefits to subjects and others. Discuss the importance of the knowledge gained or to be gained as a result of the proposed research and why the risks are reasonable in relation to the knowledge that reasonably may result. If there are no benefits state so.

Risks and Procedures to Reduce Risks

First, there are no adverse effects anticipated for participation in the questionnaires. We use questionnaires widely used in psychological studies in adolescents. In addition, there are no adverse effects anticipated from learning evidence-based behavior change skills. Teaching behavior changes skills is a commonly used evidence-based strategy to increase health behavior change in children and adolescents. Participating in these tasks, surveys, and skills pose no more risk than that experienced in the everyday lives of adolescents, e.g., reading, learning, answering questions, solving puzzles. Should any participants report discomfort with these activities we will both provide access to a list of national resources for mental and diabetes health as well as physical activity supports and the RA participating in the assessment or intervention program can provide in-the-moment support and debriefing supervised by the PI who is a licensed clinical psychologist.

Second, there is also minimal risk associated with involvement in the physical activity incentives program, such as, for example, overexertion when increasing physical activity or changes in glucose levels during and after physical activity. The level of physical activity promoted in this study does not exceed typical activity levels beyond what adolescent already participate in during everyday life (30 minutes physical activity in a day is only half of the CDC and AHA recommendation 60 minutes of daily physical activity for children and adolescents) including physical education classes and is less than would be experienced in many sports. Participation in this program brings no more risk than adolescents already experience in everyday life physical activities (e.g., walking, playing basketball, riding a bike). For adolescents with type 1 diabetes, decreases in blood glucose often occur following physical activity, and as in all daily life activities for persons with diabetes, adolescents will need to manage high and low blood glucose levels through changes in physical activity. To encourage optimal diabetes management during the program, education and support are provided. In the introduction to the Activate Program, the ADA recommendations for managing glucose levels during physical activity are reviewed as well as participants responsibility to communicate with their diabetes provider about any possible changes in diabetes management plans throughout participation, following standard care recommendations for type 1 diabetes. Learning to manage diabetes through physical activity is a key feature of all diabetes education that families participate in with their diabetes providers. Our text-based program also includes reminder to treat low and high blood glucose before exercise. Physical activity programs for youths with type 1 diabetes have been shown to be feasible, acceptable, safe, and health promoting (Knox et al., 2019; Quirk et al., 2018; 2020, Chetty et al., 2019; Marshall et al., 2020).

Third, risks of the project include the potential risk to confidentiality; however, this risk is attenuated through consistent data management. All study data will be confidential and accessible only by IRB-approved study personnel. Results from the online surveys, computerized behavior tasks, and physical assessment will be entered directly into the password-protected study database and/or stored on secure UVM servers. Each participant will be assigned a unique identification code (study ID) to maintain confidentiality. Participants' names, contact information (telephone number and e-mail address), informed consent documents, and payment form and a document that is the master list (key to the code) describing each participant's ID number will be kept in a secure file through RedCap separate from questionnaire and other study data. Participation will entail using participants' e-mail address and/or telephone number to send study surveys and from some the text message communication in the intervention program. This information will not be combined with deidentified data. During the consent process, we will inform all potential participants that, if they decide to participate, we will use their telephone number and e-mail address in order to deliver our text message program and send links to surveys. Participants contact information will remain confidential and will not be accessible by anyone other than those previously described. All research personnel will receive training in confidentiality.

Potential Benefits of the Proposed Research to Subjects- No benefits can be guaranteed, however, participants may directly benefit if assigned to the Activate group as in our pilot work and existing studies behavior change skills and physical activity improved behavior regulation, glycemic outcomes and cardiovascular health. Overall, the risks are minimal

whereas the potential benefits to the participants are substantial. We therefore find the risk-to-benefit ratio to be acceptable.

Importance of the Knowledge to be Gained – The knowledge to be gained is of scientific and practical importance. Participants may also indirectly benefit by contributing to the gathering of data to develop more effective interventions for adolescents with type 1 diabetes. We believe the new scientific information to be gained outweighs the minimal risks involved in the project.

Therapeutic Alternatives: List the therapeutic alternatives that are reasonably available that may be of benefit to the potential subject and include in the consent form as well.

Not Applicable

If parents/guardians do not wish their adolescent to participate in the study, but do wish to seek help for any diabetes management problems their adolescent may be having, they can contact their adolescent's pediatric endocrinology doctor for assistance.

Data Safety and Monitoring: The specific design of a Data and Safety Monitoring Plan (DSMP) for a protocol may vary extensively depending on the potential risks, size, and complexity of the research study. For a minimal risk study, a DSMP could be as simple as a description of the Principal Investigator's plan for monitoring the data and performance of safety reviews or it could be as complex as the initiation of an external, independent Data Safety and Monitoring Board (DSMB). The UVM/UVM Medical Center process for review of adverse events should be included in the DSMP.

Data and Safety Monitoring Plan –As noted above, risks associated with this study are minimal and are not believed to exceed those adolescents already encounter in daily life. Specifically, the behavior change skills training and physical activity program is designed to help participants come closer to meeting the widely accepted guideline of engagement in at least one hour of moderate intensity physical activity each day (AHA and CDC^{61,62}). This level of involvement is believed necessary to yield optimal health benefits in persons with diabetes (ADA⁶⁴). Consequently, given the minimal risk nature of the protocol, the primary monitor of the data and participant safety will be Drs. [name]; this monitoring will occur on an ongoing basis, with the status of participant adolescents discussed at weekly meetings. Any adolescent experiencing difficulty with the physical activity program will be referred via the adolescent's parents to their physician for evaluation. The research team will document and review any adverse events that occur for each participant during the study. At baseline and 12-week follow up appointments, a research assistant will complete an adverse event form with the participant where they will be asked about any adverse events they have experienced over the past 3 months, in order to compare adverse events pre and post study, and between study conditions. Participants randomized to the intervention program will also have access to the adverse events form throughout the study period for additional reporting should they require it. We will also have an independent medical monitor review our summary of adverse event reports. Any adverse event will be reported to the local Institutional Review Board (IRB) in accordance with local guidelines. In addition, [name] will be responsible for assembling the study data and assisting in the preparation of annual data and safety monitoring reports. She will ensure that all monitoring plan personnel obtain copies of these reports in a timely fashion, prior to the deadline for each review. [name] will also oversee all communications with the Office of Research Protections to specifically include initial study approval; ongoing continuation reviews; and any necessary reporting of protocol deviations, protocol modifications, personnel changes, or adverse events.

Define criteria to be used for decision making regarding continuation, modification, or termination of the entire study (not individual participation) (i.e. "stopping rules").

Diabetes behavior change skills training and physical activity promotion with incentives are standard health behavior change strategies with a strong evidence base in adolescents and adults. We have also pilot tested these intervention components to address issues of feasibility and acceptability. Thus, we do not anticipate any early stopping or termination of the entire study. We will engage in continuous review of feedback from participants and if any substantial patterns arise in attrition, feasibility or acceptability, we will pause recruitment to revise intervention components to address those concerns. Following modification to intervention, recruitment would continue and continuous review of feedback from participants will begin again. Should unexpected adverse events arise we will coordinate with our research team and UVM Research Protections Office to identify the appropriate plan of action including: 1) continuation of the trial using the current protocol, 2) continuation of the trial with modifications, 3)

placing the trial on hold until clarifications requested by the UVM Research Protection Office are resolved, or 4) termination of the trial.

What will be the frequency of the review? Please note that the frequency of reviews should be commensurate with the risk of the study. At a minimum, a review of the data should be conducted annually at time of continuing review. **Forward copies of the data and safety monitoring reports to the 1) IRB, 2) CRC (if applicable), and/or 3) UVMCC (if applicable).**

Monthly
 Quarterly
 Bi-annually

Annually

Other (e.g. by dosing level, no. of subjects enrolled):

Will the sponsor be conducting data monitoring visits for this study?

Yes No NA

If yes, how often?

Adverse Event, Unanticipated Problem (UAP), Reportable New Information (RNI): Describe how events and UAPs will be evaluated and reported to the IRB. All protocols should specify that, in the absence of more stringent reporting requirements, the guidelines established in the "Adverse Event and Unanticipated Problems Reporting Policy" will be followed. The UVM/UVM Medical Center process for review of adverse events and UAPs to subjects or others should be included in the DSMP.

Should any adverse events, unanticipated problems or reportable new information arise, the PI will contact the IRB according to the Adverse Event and Unanticipated Problems Reporting Policy using the UVM Reporting Form.

Withdrawal Procedures: Define the precise criteria for withdrawing subjects from the study. Include a description of study requirements for when a subject withdraws him or herself from the study (if applicable).

At any time, a participant can choose to withdraw from participation. We do not anticipate withdrawing any adolescent from the study but reserve the right to do so under unforeseen circumstances. These might include situations such as discovery of a medical problem indicating the adolescent should not participate in physical activities. If a participant is withdrawn or withdraws from participation their data will not be included in analyses.

Sources of Materials: Identify sources of research material obtained from individually identifiable human subjects in the form of specimens, records or data. Indicate whether the material or data will be obtained specifically for research purposes or whether use will be made of existing specimens, records or data.

All data is being collected solely for research purposes. Participants will provide dried blood spot assays, measurements of abdominal circumference and blood pressure as well as complete computerized self-report questionnaires. This data will be coded at the time of collection.

DRUG INFORMATION

Investigators are encouraged to consult the UVM Medical Center Investigational Pharmacy Drug Service ([name]) prior to finalizing study drug/substance procedures.

Drug (s)

Not applicable

Drug name – generic followed by brand name and common abbreviations. Availability – Source and pharmacology; vial or product sizes and supplier. If a placebo will be used, identify its contents and source.

Preparation: Reconstitution instructions; preparation of a sterile product, compounded dosage form; mixing guidelines, including fluid and volume required. Identify who will prepare.

Storage and stability – for both intact and mixed products.

Administration – Describe acceptable routes and methods of administration and any associated risks of administration.

Toxicity – Accurate but concise listings of major toxicities. Rare toxicities, which may be severe, should be included by indicated incidence. Also, adverse interactions with other drugs used in the protocol regimen as well as specific foods should be noted. Address significant drug or drug/food interactions in the consent form as well. List all with above details.

Is it FDA approved: (include FDA IND Number)

1. in the dosage form specified? If no, provide justification for proposed use and source of the study drug in that form.
2. for the route of administration specified? If no, provide justification for route and describe the method to accomplish.
3. for the intended action?

**SUBJECT CHARACTERISTICS,
IDENTIFICATION AND
RECRUITMENT**

Subject Selection: Provide rationale for subject selection in terms of the scientific objectives and proposed study design.

This study examines an intervention to reduce health disparities for adolescents with type 1 diabetes and socioeconomic disadvantage. Our goal is to recruit a heterogeneous sample of families with and without SED to achieve a comparison of this intervention's feasibility with adolescents with type 1 diabetes and SED. We will recruit 60 adolescents aged 13-17 years old with type 1 diabetes, through a mixed clinic-based and national advertising recruitment method established with our research team that leverages Facebook, Instagram, and Google Ads resulting in a nationally representative sample (see attached advertisement). We believe these recruitment strategies will allow us to obtain a heterogeneous sample. Inclusion criteria will be the adolescents being at least 18 months post-diagnosis (due to a "honeymoon" period for glycemic outcomes in the first year after diagnosis), parent reported moderate to no physical activity for adolescent, ability to complete measures and intervention program in English, access to broadband or cellular internet, and currently residing in and receiving healthcare in the United States. In order to recruit a heterogeneous sample that aligns with our research goals, we will modify our recruitment criteria after we have enrolled 30 participants in the study. This modification will include the addition of the following inclusion criteria: adolescent is from a marginalized racial or ethnic group. Exclusion criteria will be ward of state, active psychosis, severe medical or psychiatric illness that limit participation (including any contraindications for physical activity per parent report on the physical activity readiness questionnaire). We are specifically recruiting adolescents aged 13-17 with type 1 diabetes and socioeconomic disadvantage due to the specific developmental challenges associated with disease management during this developmental period and the importance of this period for reducing future health disparities.

Vulnerable Populations: Explain the rationale for involvement of subjects (e.g., cognitively impaired, Non-English speaking, prisoners, students). Discuss what procedures or practices will be used in the protocol to minimize their susceptibility to undue influences and unnecessary risk (physical, psychological, etc.).

Not applicable

